#### **Exclusion criteria:**

1. Younger than 18 y;
2. Inability to sign informed consent.

### **Procedures**

#### **I-MIBG Imaging Acquisition**

**HP00043324**  
**NCT01250912**

All subjects will be pretreated with either perchlorate (potassium or sodium) or an iodine solution to block uptake of free iodine ( $^{123}\text{I}$ ) by the thyroid gland. For the imaging study, an activity of 370 MBq (10 mCi)  $^{123}\text{I}$ -mIBG (GE Healthcare) will be administered intravenously, and a 10-minute planar image of the anterior thorax (128\_128 matrix) will be acquired beginning 15 minutes after tracer injection. A SPECT study will then be acquired using either a dual- or triple-head gamma camera (minimum 30 projections/head, 20 to 30 seconds/ projection, 64\_64 matrix). Repeat planar image and SPECT studies will be acquired at 4 hours after injection. All camera heads will be equipped with low-energy, high-resolution collimators, and all acquisitions will be performed with a 20% energy window centered at the 159 keV photopeak of  $^{123}\text{I}$ . Images will be reacquired 6 months after the ablation.

**$^{123}\text{I}$ -MIBG Imaging Reconstruction and Integration**

The SPECT dataset will undergo post-procedural DICOM3 formatting analogous to the CT or MRI datasets using MATLAB 7.6.0 (The Mathworks Inc.). The formatted SPECT dataset will be transferred into the electrophysiology mapping system using the CartoMERGE Image Importation algorithm.

**Voltage Map Dataset**

All voltage maps will be created by an electrophysiologist using a Carto 3D mapping system and a 3.5-mm Navistar cooled-tip catheter. Bipolar electrograms will be filtered at 10–30 to 400–500 Hz. Standard clinical voltage criteria will be used to define scar (<0.5 mV), abnormal (0.5–1.5 mV), and normal (>1.5 mV) myocardium. Each voltage map will be divided into 17 segments according to the AHA LV model to conduct visual analysis as well as quantitative analysis.

**HP00043324**  
**NCT01250912**

### **123I-MIBG Imaging Dataset**

For the planar images a whole-heart region of interest (ROI) will be drawn manually to include both ventricles. A square mediastinal ROI (7x7 pixels) will be drawn in the upper mediastinum, using the apices of the lungs as anatomic landmarks. The H/M ratio will be calculated as the ratio of the counts per pixel in the two ROIs. H/M data will be used to calculate myocardial washout using two formulas. Uncorrected washout will be calculated as

$$H/M (early) - H/M (late) / H/M (early).$$

Background corrected washout will be calculated as

$$H (early) - M (early) - H (late) - M (late) / H (early) - M (early)$$

Single aggregate values for each washout parameter will be determined as described above.

For the SPECT image sets, segmental myocardial activity will be scored using a 17-segment model. Each segment will be scored using the following scale: 0 normal tracer uptake, 1 mildly reduced uptake, 2 moderately reduced uptake, 3 severely reduced uptake, 4 absent tracer uptake, NA not assessable. Accordingly, the summed score (SS) for each study could range from 0 to 68 (17x4).

### **Heart Rate Variability**

All the patients will undergo 24-hour ambulatory electrocardiographic monitoring on entrance into the study in order to investigate the prognostic value of heart rate variability (HRV). Time and frequency domain HRV parameters will be calculated from those recordings. Traditional measurements of HRV will be analyzed according to the Task Force of the European Society of Cardiology and the North American society of Pacing and Electrophysiology. Time domain analysis of HRV will include the mean duration of

**HP00043324**  
**NCT01250912**

all normal-to-normal (NN) intervals (mean RR), standard deviation of all normal-to-normal intervals (SDNN), standard deviation of the averages of NN intervals in all 5-min segments, mean of SDNN in all 5-min segments (SDNN index), square root of the mean of the sum of the squares of differences between adjacent NN intervals, number of NN intervals differing by more than 50 ms from the adjacent interval divided by the total number of NN intervals, and HRV triangular index. HRV parameters will be reacquired 6 months after the ablation.

**Patient Characteristics**

Patient clinical characteristics (gender, age, ejection fraction, comorbidities, anti-arrhythmia medications) and their clinical VT characteristics (morphology, frequency, duration, cycle length, termination strategy, previous ICD shocks) will be collected.

**Research Part of the Protocol**

Four specific aims were plan to achieved for this research. Specific Aim 1: Evaluate if areas of left ventricular (LV) denervation measured by cardiac 123I-metaiodobenzylguanidine (MIBG) SPECT imaging (innervation map) can be integrated into the CartoXP electrophysiology mapping system. Specific Aim 2: Evaluate, in a group of 20 patients, if areas of denervation in the 3D maps reconstructed from MIBG SPECT imaging correlate with the voltage-map defined scar targeted during VT ablations Specific Aim 3: Determine the changes of cardiac innervation before and 6 months after the VT ablation in 20 patients. Specific Aim 4: Investigate the possible predicting factors for VT reoccurrence within six month after the ablation.

**Risks**

**HP00043324**  
**NCT01250912**

Ventricular tachycardia ablation procedures have a definite morbidity and mortality, with a major complication rate of endocardial procedures ranging from 2.5 to 6 %. This is due to both patient-related and procedure-related factors. Patients typically suffer from congestive heart failure and other comorbidities and the procedures are long, requiring the patient to lie flat for up to eight hours at times. It must be emphasized that both procedures are currently performed on patients as indicated.

In addition to the risks of sedation, standard risks of an endocardial procedure include bleeding and other vascular access complications, stroke, myocardial infarction and rarely myocardial rupture and pericardial tamponade, aortic valve avulsion, and entanglement of the catheter in the mitral valve apparatus requiring surgical intervention, and death. Attempts to ablate VT using an endocardial-only approach in patients with a high likelihood of having an epicardial origin would lead to unnecessarily prolonged endocardial procedures and failed ablation. This would lead to a second, epicardial, procedure.

**Measures to Reduce Risks**

Our approach will be to conduct the cardiac imaging scan and reconstruction for the patients first. This will be followed by endocardial mapping. The imaging information known before the endocardial procedure will help reduce the mapping time, improve the mapping/ablation accuracy and reduce the risk due to the long procedure time. It is our belief that, with this imaging guidance approach, we can improve the success rate of VT ablation in VT patients.

**Data Analysis**

Means and standard deviations will be calculated for each of the four registration strategies, i.e. LM, LM and SF, VA, VA and SF, in order to identify the best registration method.

**HP00043324**  
**NCT01250912**

Differences in scar size, morphology and severity between 3D MIBG innervation maps and EP voltage maps will be analyzed using Student T-test. Segments where diastolic potentials, fractionated potentials and successful ablation sites are located will be investigated in order to identify the characteristics of the MIBG imaging in those segments, e.g. heterogeneity, etc. Segmental/regional washout rate, normalized MIBG activities as well as SS scores will be compared with segmental/regional voltage values in order to identify the relationship between cardiac denervation areas and abnormal endocardial voltage areas.

Differences in size, morphology and severity, regional/global washout from planar images, normalized regional intensities, regional activity summed scores between pre and post ablation 3D MIBG innervation maps will be analyzed using Paired T-test. Global wash out rate will be correlated with HRV indexes before and after the ablation to investigate the relationship between them. Normalized regional MIBG intensities, regional wash out rate and regional SS score both before and after ablations will be compared between VT exit sites segments and other segments with independent sample T-test in order to identify the innervation characteristics of the exit site segments.

Measurements and results will be reported as mean  $\pm$  standard deviation if a normal distribution can be assumed. P values at a level of  $<0.05$  will be considered as statistically significant. Pearson correlation will be conducted to investigate the relationship between two sets of images. The logistic regression will be conducted to investigate the relationship between 3D innervation morphologies, HRV parameters, patient characteristics, clinical VT characteristics and the VT recurrence within the six month

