**HP00043324**  
**NCT01250912**

follow-up period. Receiver operating characteristics (ROC) curves will be used to assess best correlation performed with innervation and voltage map.

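### The MIBG-versus-voltage Student t-test has no common scale for severity, does not state pairing for size, and leaves per-patient agreement in size unreported

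*Combined protocol and SAP*

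**What the plan says.** The MIBG-versus-voltage comparison in Data Analysis reads: "Differences in scar size, morphology and severity between 3D MIBG innervation maps and EP voltage maps will be analyzed using Student T-test". The next paragraph is more specific about its own tests. Pre- and post-ablation differences "between pre and post ablation 3D MIBG innervation maps will be analyzed using Paired T-test", and MIBG values are "compared between VT exit sites segments and other segments with independent sample T-test". Morphology appears again in that pre/post comparison ("Differences in size, morphology and severity, regional/global washout from planar images") and in the logistic regression, which is to "investigate the relationship between 3D innervation morphologies, HRV parameters, patient characteristics".

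Measurements are to be summarised as mean and "standard deviation if a normal distribution can be assumed". Three other analyses link the maps:
- "Pearson correlation will be conducted to investigate the relationship between two sets of images".
- ROC "curves will be used to assess best correlation performed with innervation and voltage map".
- A segmental or regional comparison of washout, normalised MIBG activity and summed scores with voltage values, with no method named.

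The 123I-MIBG Imaging Dataset section scores each of 17 segments from 0 (normal) to 4 (absent uptake), or NA. The Voltage Map Dataset section uses the same 17-segment layout and classes voltage as scar (<0.5 mV), abnormal (0.5–1.5 mV) or normal (>1.5 mV). Specific Aim 2 concerns 20 patients. Measures to Reduce Risks says that imaging comes first and endocardial mapping follows, so each patient supplies both maps.

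**The concern.** A t-test of a difference needs two measurements in the same unit. For severity the documents give none: a five-level score rising with damage on one side, and millivolts falling with damage, or three classes, on the other. Whatever p-value came out could not be read as agreement or disagreement between the maps.

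For size, the unqualified name of the test leaves a programmer to choose. An unpaired run on paired data would usually lose power, and a non-significant result could then be taken as a sign that the maps match. Even a paired p-value says only whether the average sizes differ. The stated objective is better guidance of ablation, so the spread of the difference from patient to patient matters too. No confidence interval or limits of agreement are planned for it. MIBG size also has no stated threshold: four score cut-offs (≥1 to ≥4), or a cut-off on normalised activity, would all fit the text.

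**Working it through.** The plan states no power, SD, effect size or correlation, so it has no figure to reproduce. Only n=20 and the 0.05 level come from the documents. Two-sided testing, equal SDs on both maps, normality and the correlations ρ are assumptions.

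**Severity.** Take the literal reading, score minus voltage, and two illustrative segments, one at 2.0 mV and one at 0.4 mV.
- Concordant (scores 0 and 4): differences 0 − 2.0 = −2.0 and 4 − 0.4 = 3.6; mean 0.8.
- Scores swapped, fully discordant: 4 − 2.0 = 2.0 and 0 − 0.4 = −0.4; mean again 0.8.
- Concordant, in microvolts: 0 − 2000 = −2000 and 4 − 400 = −396; mean −1198.
- Concordant, with the worse segment graded 3 instead of 4: −2.0 and 2.6; mean 0.3, although the ranking is unchanged.

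The mean difference follows the unit and the grading cut-points and ignores which segments are affected. With patient means as the data, moving scores among a patient's segments cannot change the p-value at all. With segments as the data the p-value can change, but the mean difference still ignores location.

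**Size: pairing.** With SD = 1 on each map, the SD of the within-patient difference is SDd = √(2(1 − ρ)). The paired test has 19 df (critical t 2.093) and noncentrality 0.5 × √20 / SDd. The unpaired pooled test has 38 df (critical t 2.024); its behaviour on correlated data was simulated.

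| ρ | SDd | noncentrality | power, paired | power, unpaired | type I error, unpaired |
|---|---|---|---|---|---|
| 0 | 1.414 | 1.58 | 32% | 34% | 5.0% |
| 0.3 | 1.183 | 1.89 | 43% | 31% | 2.1% |
| 0.5 | 1.000 | 2.24 | 56% | 29% | about 0.7% |
| 0.7 | 0.775 | 2.89 | 78% | 25% | 0.1% |

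For a true difference of 1.0 SD the gap is small: 91%, 94% and 97% unpaired against 95%, 99% and 100% paired at ρ = 0.3, 0.5 and 0.7.

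The 95% CI half-width of the mean difference is 2.024 × √(2/20) = 0.64 SD unpaired, whatever ρ is. Paired, it is 2.093 × SDd / √20 = 0.55, 0.47 and 0.36 SD at the same three correlations.

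**Size: agreement.** Limits of agreement are the mean difference ± 1.96 × SDd. For the same two means and SDs this is ±2.77, ±2.32, ±1.96, ±1.52 and ±1.24 SD at ρ = 0, 0.3, 0.5, 0.7 and 0.8. The two map-wise means and SDs alone therefore do not fix per-patient agreement. Pearson's r does not show offset either: if MIBG size = a + b × voltage size with b > 0, r is 1 for every a and b.

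**The case against.** The strongest reply is that Aim 2 asks whether the areas correlate, and the plan analyses that through Pearson correlation, ROC curves and the segmental comparison with voltage. This stands. A reader might infer that a faulty t-test leaves Aim 2 without an analysis. It does not; the segmental comparison lacks a named method, but it is planned.

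Second, the plan never says that a score will be subtracted from millivolts. It also mentions normalised MIBG activity and voltage classes. That is right, and the arithmetic above shows one assumed reading. But normalised activity is not in mV either, and five score levels do not map onto three voltage classes without a rule. No reading in the documents supplies a common scale.

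Third, a reader might infer that the size test will be unpaired, because the next paragraph uses the word paired where it wants it. That paragraph equally labels its independent-sample test, so the text does not settle the question. The power loss is conditional on an unpaired run.

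Fourth, limits of agreement might be recovered from ordinary reporting. If a paired test is run and the mean difference d and exact p are given, SDd = |d| × √20 / t. Reporting the difference itself as mean ± SD also suffices. The plan commits to neither, so this narrows the point without removing it.

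Finally, limits of agreement are an addition in a 20-patient exploratory study, and MIBG minus voltage is not MIBG error. The Background says MIBG shows innervation and that voltage mapping can overestimate scar. Both remarks are fair. The difference should be described as a difference, and its spread is still needed if one map is to guide work done on the other.

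**Conclusion.** The concern holds in limited form. The severity t-test is not interpretable as specified; that needs no numerical assumption beyond the scales in the documents. Morphology cannot enter a t-test until it has a numeric measure. For size, pairing is unstated. If the test were run unpaired, power for a 0.5 SD difference would fall by about 12, 28 and 53 percentage points (43 − 31, 56 − 29 and 78 − 25, from unrounded values) at assumed correlations of 0.3, 0.5 and 0.7. There would be no loss near zero correlation and little at 1.0 SD. No planned analysis is committed to showing per-patient agreement in size. The documents do not support the stronger readings that Aim 2 is unanalysed, that an unpaired test has been chosen, or that any size difference is an error of MIBG. The sponsor should make the change; the study is not invalid without it.

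**What to change.** In Data Analysis, replace the MIBG-versus-voltage t-test sentence as follows.

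- **Size.** Compare by a paired t-test on the per-patient difference, MIBG defect area minus voltage scar area (<0.5 mV, as already defined). Express both as a percentage of LV surface or both as a segment count. Report the mean difference with 95% CI and Bland-Altman limits of agreement.
- **MIBG threshold.** Fix it before analysis, and do not take it from the ROC curve in the same patients, which would tune it to match voltage. Otherwise show the difference descriptively at each score cut-off, without four significance tests.
- **Severity.** Drop the t-test. Name the method for the segmental comparison already planned: the within-patient Spearman correlation of segment score (or normalised activity) with segment voltage, averaged over patients with 95% CI. Exclude NA segments and report in how many patients it cannot be computed.
- **Morphology.** Remove it from the t-tests unless a numeric measure is defined.
- **Keep** Pearson and ROC.

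The cost is plan wording and minor analysis of data already to be collected. The drawback is precision: at n=20 each limit of agreement has a 95% CI of about 2.093 × √(1/20 + 1.96²/38) = ±0.81 SD of the differences, so the limits will be rough and should be reported with that interval.

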**Protocol**

**09/16/09**

**Background**

VT is the next frontier in electrophysiology. An increasing number of patients require VT ablation despite optimal medical therapy. Myocardial scars are present in the majority of patients with ischemic and nonischemic cardiomyopathy and usually act as the substrate for reentrant VT. According to pathological findings, rather than being homogeneous tissue, cardiac scars often contain many “channels” of surviving myocardium within the area, which enable electricity to enter, traverse, and exit the scar via different connections within this network and form a “reentry loop” maintaining reentrant VT. Cauterizing the myocardial channels along the scar border in order to interrupt those loops and clinical VT, therefore, is the aim for most reentrant VT ablations. Because of hemodynamic intolerance as well as the pre-existing alternative channels and exit sites, an approach targeting single VT channels identified by their electrical characteristics will not be applicable for the majority of patients. A “substrate-guided” ablation approach is frequently conducted to treat such arrhythmias and involves the placement of linear ablation lesions along the scar

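### The exit-site comparison on the 6-month scan mixes an effect of ablation with whatever innervation the exit sites had beforehand, so only the pre-ablation scan can serve its stated purpose.

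*Combined protocol and SAP*

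**What the plan says.** Data Analysis states that three regional measures, namely the SS score, the normalized MIBG intensity and the washout, "both before and after ablations will be compared between VT exit sites segments and other segments". The method is a t-test for independent samples, and it is carried out "in order to identify the innervation characteristics of the exit site segments". One test and one purpose cover both time points. The imaging acquisition section fixes the later one: "Images will be reacquired 6 months after the ablation".

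Three other statements bear on how the later comparison can be read.

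- The Background gives the aim of most reentrant VT ablations: "Cauterizing the myocardial channels along the scar border in order to interrupt those loops and clinical VT". It describes the channels concerned as those that "enable electricity to enter, traverse, and exit the scar via different connections within this network".
- Specific Aim 3 is to "Determine the changes of cardiac innervation before and 6 months after the VT ablation in 20 patients", so the plan itself allows that innervation may differ after ablation.
- Data Analysis compares several measures "between pre and post ablation 3D MIBG innervation maps will be analyzed using Paired T-test". That comparison is not split by exit-site status or by ablation status.

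Data Analysis also examines the MIBG features of segments containing successful ablation sites. It does not use those locations to exclude segments from the exit-site comparison or to adjust it.

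**The concern.** Identifying the innervation characteristics of exit sites means describing a feature of the tissue that supports the arrhythmia. The pre-ablation scan can show this. By six months the same tissue may carry lesions, and the plan's account of where lesions go suggests that exit-site segments receive them more often than the rest of the ventricle. If lesions alter MIBG uptake or washout locally, a difference on the later scan need not be something the exit sites had before treatment.

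The study's objective is better guidance for ablation, and for that the pre-ablation appearance matters. A post-ablation difference read under the stated purpose could credit exit sites with a deficit made by the procedure, or make a small pre-existing deficit look larger. More patients or a different test would not remove the problem, because it lies in what is being compared.

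**Working it through.** The plan gives no effect size, standard deviation or power for this comparison, so there is no figure to reproduce.

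**What the 6-month contrast estimates.** Let D be the pre-ablation mean difference between exit-site and other segments, L the mean change a lesion causes in a segment, and pE and pO the shares of exit-site and other segments ablated. If L is the same in both groups and other changes over six months are equal on average:

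- pre-ablation difference = D
- 6-month difference = D + L × (pE − pO)
- difference in change from baseline = L × (pE − pO)

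The pre-ablation scan gives the quantity wanted. The 6-month scan adds a second term, which is zero only if lesions have no effect or both groups are ablated equally often. It reverses sign if other segments are ablated more often. The change from baseline isolates that second term, which describes ablation and not exit sites.

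**Illustration on the 0–4 segment score.** From the documents: 20 patients, 17 segments, significance level 0.05 (taken as two-sided). Assumed: D = 0; 2 exit segments per patient, giving 40 exit and 300 other segments; all exit segments ablated (pE = 1); k of the 15 other segments ablated in each patient (pO = k/15); SD 1.2; segments independent.

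Spurious difference = L × (1 − k/15). SE = 1.2 × √(1/40 + 1/300) = 0.202. The probability of p < 0.05 is by normal approximation.

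| L (points) | k = 2 | k = 6 |
|---|---|---|
| 1.0 | 0.87 points, 99% | 0.60 points, 84% |
| 0.5 | 0.43 points, 57% | 0.30 points, 32% |
| 0.25 | 0.22 points, 19% | 0.15 points, 12% |

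For example, with L = 0.5 and k = 2: 0.5 × (1 − 2/15) = 0.43, and 0.43/0.202 = 2.1 standard errors.

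**Sensitivity by simulation.** The planned t-test was simulated with D = 0 and every exit segment ablated, 1,500 runs per setting. Within-patient correlation was 0 or 0.3, and scan-to-scan noise was 0.3 SD. For a lesion effect of 0.5 SD, the share of runs significant at 6 months was:

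| Other segments ablated | 1 exit segment per patient | 2 exit segments per patient |
|---|---|---|
| 0% | 54–56% | 83–85% |
| 20% | 36–37% | 62–65% |
| 50% | 13–15% | 24–27% |

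The mean spurious difference followed the formula: 0.5 × (1 − 0.2) = 0.40 SD and 0.5 × (1 − 0.5) = 0.25 SD, against simulated values of about 0.40 and 0.24 to 0.25. With a 0.25 SD effect and half of the other segments ablated, 4 to 10% of runs were significant. With a 1.0 SD effect and no other segments ablated, 98 to 100% were.

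The pre-ablation test in the same simulations rejected in about 4 to 6% of runs with correlation 0 and 1 to 3% with correlation 0.3. Lesions cannot affect it.

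**The case against.** Several points on the other side have force.

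**How far exit sites are preferentially ablated is inferred.** The documents do not define an exit site, do not say that every exit-site segment is ablated, and do not give the share of other segments ablated. The Background describes linear lesions meant to interrupt as many channels as possible, and such lines may cross many non-exit segments. Data Analysis also names successful ablation sites separately from exit sites. A reader might infer that the 6-month contrast is essentially ablated versus non-ablated tissue. The documents do not support that; they support only a likely imbalance of unknown degree.

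**The pre-ablation comparison is kept.** A reader might also infer that a lesion-made deficit would pass for confirmation of a pre-ablation finding. If exit sites had ordinary innervation before treatment, there would normally be no such finding to confirm, and the artefact would appear as absent before and present after. Anyone setting the two results side by side would have a warning. This stands, but the plan does not prescribe that reading and gives both results the same purpose.

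**The later comparison may be descriptive.** It follows the pre/post paired test and could be meant as a description of exit segments at each time point, in keeping with Aim 3. That is a fair alternative reading. It does not fit the single stated purpose, and if change is the question, the plan specifies no contrast of change between exit-site and other segments.

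**The probabilities rest on assumptions.** Nearly every input beyond 20 patients, 17 segments and the 0.05 level is assumed. The score is capped at 4, so a segment already scoring high has little room to worsen, and the illustration ignores this. The figures show a range and are not a forecast.

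**The analysis is not central.** None of the four aims names the exit-site comparison, and no decision rule depends on it. This limits the weight of the point.

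**Conclusion.** The point holds as a modest improvement. Applied as written, the 6-month comparison does not answer the question set for it, because any difference combines a pre-existing exit-site property with a lesion effect, and nothing in the plan separates the two. The pre-ablation comparison is not affected by this problem, so the exit-site analysis as a whole is not invalid.

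The bias equals the lesion effect multiplied by the difference in ablated share, assuming equal lesion effects in the two groups and no other differential change over six months. Both factors are unknown. Under the assumptions above, the chance of a significant 6-month result with no true pre-ablation difference runs from about 4% to essentially 100%, so no single figure should be quoted. The conclusion rests on two inferences from the plan's own text: that exit-site segments are ablated more often than others, and that ablation may change local innervation.

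**What to change.** In Data Analysis:

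1. Base the identification of exit-site innervation characteristics on the pre-ablation scan only.
2. Report the 6-month data under Aim 3 as the within-segment change from baseline in exit-site versus other segments.
3. Label that change as including the effect of ablation, and state that it is not to be read as an exit-site characteristic.
4. Where segmental lesion location is recorded, split the change by ablated versus non-ablated segments.

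Items 1 to 3 are wording changes that use scans already planned, with no added patients or imaging. Item 4 needs a per-segment record of all lesions. The plan mentions only the segments containing successful ablation sites, so a full record cannot be assumed, and the split is conditional for that reason. The price is that the post-ablation cross-sectional test is no longer used as evidence about exit sites.

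### Exit-site and other segments of the same hearts are compared with an independent-sample t-test, so the p-value can be wrong in either direction; Aim 2 does not state its unit of analysis

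*Combined protocol and SAP*

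**What the plan says.** Under Data Analysis, three regional measures (normalised MIBG intensity, washout rate and SS score), each before and after ablation, "will be compared between VT exit sites segments and other segments with independent sample T-test". That makes 3 × 2 = 6 comparisons, and p<0.05 is declared significant.

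Both imaging datasets use 17 segments per heart. Under Voltage Map Dataset: "Each voltage map will be divided into 17 segments according to the AHA LV model". Under 123I-MIBG Imaging Dataset, each segment is scored from 0 to "4 absent tracer uptake, NA not assessable". The sample appears in Specific Aim 2 under Research Part of the Protocol: "Evaluate, in a group of 20 patients".

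Data Analysis does recognise pairing for the before-and-after comparison: "regional activity summed scores between pre and post ablation 3D MIBG innervation maps will be analyzed using Paired T-test".

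For Aim 2 it says "Segmental/regional washout rate, normalized MIBG activities as well as SS scores will be compared with segmental/regional voltage values", without tying a method to that sentence. It then adds "Pearson correlation will be conducted to investigate the relationship between two sets of images" and "Receiver operating characteristics (ROC) curves will be used to assess best correlation performed with innervation and voltage map". None of these sentences says whether an observation is a segment or a patient. No patient term, clustering adjustment or per-patient summary appears anywhere.

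**The concern.** A heart with an exit site also supplies the other segments it is compared with. The two groups are therefore paired within patient, and segments of one heart are likely to resemble each other. An independent-sample t-test is wrong on either reading of the sentence: pooling segments ignores the clustering, and averaging per patient first produces paired columns whose pairing is then discarded. Because a paired test is named elsewhere in the same section, this is not just loose terminology.

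At stake is whether the exit-site p-values can be read at 0.05. This is the only formal comparison named for the innervation characteristics of exit-site segments, which bears on the study objective of guiding ablation.

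For Aim 2 the concern is conditional. If segments are pooled, up to 20 × 17 = 340 values from 20 patients would be treated as independent. A measure that keeps each patient's overall level could then correlate with voltage merely because some patients are low on both, with no spatial match. The term normalised is undefined, so it is unclear whether it removes that level.

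**Working it through.** **Inputs.** From the documents: 20 patients, 17 segments per heart, significance level 0.05 (two-sided assumed). The plan states no effect size, SD, within-heart correlation or number of exit sites, and has no power calculation to reproduce. ICCs, exit counts, contrast SDs and slopes below are therefore assumptions. Total segment SD is set to 1, with patient variance = ICC and segment variance = 1 − ICC. Results use 10,000 simulated datasets per scenario unless stated.

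**1. Equal exit counts, constant effect, segments pooled.** The patient level cancels from the difference in means, so its true variance is (1 − ICC) times what the test assumes. Hence size ≈ 2[1 − Φ(1.96/√(1 − ICC))]:

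- ICC 0.1: 1.96/√0.9 = 2.066, size 3.9%
- ICC 0.3: 1.96/√0.7 = 2.343, size 1.9%
- ICC 0.5: 1.96/√0.5 = 2.772, size 0.6%

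Simulation with two exits per heart, power for a 0.4 SD effect:

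| | ICC 0.1 | ICC 0.3 | ICC 0.5 |
|---|---|---|---|
| Pooled test, type I error | 4.0% | 2.2% | 0.7% |
| Pooled test, power | 67% | 69% | 73% |
| Per-patient means, independent t-test, type I error | 2.3% | 0.4% | <0.1% |
| Per-patient means, independent t-test, power | 55% | 38% | 22% |
| Per-patient contrast, power | 66% | 77% | 89% |

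If only 12, 16 or 20 patients have an exit site (ICC 0.5), power is 46%, 60%, 73% for the pooled test and 66%, 80%, 89% for the contrast.

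**2. Exit-site contrast varying between patients (mean zero), pooled.** Ranges are over ICC 0.1 to 0.5.

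| Contrast SD | Type I error | If the measure is centred within patient |
|---|---|---|
| 0.3 | 2-5% | 8-9% |
| 0.5 | 5-9% | 11-15% |
| 0.7 | 9-13% | 17-23% |

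**3. Exit count rising with denervation, pooled.** Exits per patient = 1 + Poisson(1.4·exp(bz − b²/2)), capped at 8, where z is the standardised patient level (mean count 2.4).

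| b | 0 | 0.2 | 0.4 | 0.6 | 0.8 |
|---|---|---|---|---|---|
| ICC 0.3 | 3.8% | 6.0% | 14.0% | 26.6% | 38.7% |
| ICC 0.5 | 3.3% | 6.9% | 20.0% | 38.9% | 55.2% |

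At ICC 0.1 the range is 5-17%. Centring within patient brings it to about 5%.

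**4. Other exit patterns (6,000 datasets each), pooled.**

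- Uneven counts of 1 to 8, unrelated to patient level: 11.5%, 15.4%, 20.0% at ICC 0.3, 0.5, 0.7.
- The same idea with eight hearts having no exit site: 17.6%, 22.6%, 29.3%.
- Three adjacent, spatially correlated exit segments (correlation 0.7): 12.1% at ICC 0, falling to 0.9% at ICC 0.7.
- No dependence of any kind: 4.9-5.4%.

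**5. The within-patient analysis.** Type I error of the per-patient contrast was 4.5-5.4% wherever tested in items 1-3 and 4.4-5.7% in item 4. On a simulated 0-4 score (3,000 datasets) the signed-rank version gave 4.8-5.3%. The independent t-test gave 4.3%, 2.5%, 1.0% at ICC 0.1, 0.3, 0.5.

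**6. Aim 2, only if segments are pooled.** With the same ICC in both maps and no spatial association, the design effect for Pearson is 1 + (17 − 1)·ICC², the effective n is 340 divided by it, and size ≈ 2[1 − Φ(1.96/√design effect)].

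| ICC | 0.05 | 0.1 | 0.2 | 0.3 | 0.5 |
|---|---|---|---|---|---|
| Design effect | 1.04 | 1.16 | 1.64 | 2.44 | 5.0 |
| Effective n | 327 | 293 | 207 | 139 | 68 |
| Simulated type I error | 6% | 7% | 12% | 20% | 38% |

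For ICC 0.5 the formula gives 1.96/√5 = 0.877, size 38%, as simulated. If the MIBG measure is centred within patient there is no inflation (4.8% falling to 0.9%). Per-patient correlations on the Fisher z scale, tested across the 20 patients, gave 4.8-5.4%.

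**The case against.** The strongest reply is that only the mismatch between test and design is certain. How far the p-value is off depends on quantities the plan does not give. With no within-heart dependence the pooled test is near nominal, and at ICC 0.1 with a constant effect it loses no power (67% against 66%). The intensity measure is called normalised; if that means centred within patient, the pooled test is close to 5% unless the contrast varies between patients. The 39% and 55% figures need a steep assumed slope. The exit-site comparison is not one of the four specific aims, and no treatment decision hangs on it. For Aim 2, the plan never says it pools.

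Most of this is right about size. It does not rescue the test. Normalisation is undefined and is attached only to intensity, not to washout or SS score. Centring makes matters worse when contrasts vary, and an independent t-test on per-patient means of a centred measure is also too liberal, at about 9-10%. Uneven exit counts alone can inflate the error. The plan gives no reason to expect independence within a heart.

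The Aim 2 point stands only as a request for clarification. One related gap belongs with it: the Student t-test of MIBG maps against voltage maps in the same patients is not said to be paired, and if run unpaired it would raise a similar problem without any pooling of segments.

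**Conclusion.** The concern holds. The named test is wrong for the exit-site comparison as written, and nothing elsewhere in the plan corrects it. Under the assumptions shown, its type I error runs from below 1% to well above 20% at a nominal 5%. The direction depends on exit counts, their relation to denervation and how much the contrast varies between patients, so the p-values cannot be relied on at 0.05. The largest figures rest on the strongest assumptions and should not set the importance of the point. What supports a correction is that a test with the right error rate is available from the same data and gains power at moderate or high ICC.

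For Aim 2 the finding is limited: the unit of analysis is not stated, and pooling would inflate Pearson error for measures that keep the patient's level. This should be fixed before analysis; it does not threaten the study as a whole.

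**What to change.** Replace the independent-sample t-test with wording such as:

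> For each patient with an identified exit site and at least one assessable exit segment and one assessable other segment, the mean of the exit segments minus the mean of the other segments will be calculated, separately before and after ablation. It will be tested against zero across patients (one-sample t-test; Wilcoxon signed-rank for the 0-4 score). The number of patients contributing will be reported.

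A linear mixed model with a random patient intercept and a random exit-site effect is an alternative, though it was not simulated here.

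For Aim 2, state the unit of analysis for the Pearson and ROC analyses, define normalised, and say whether the Student t-test of the two maps is paired. If segments are used, test per-patient correlations or slopes across patients, or fit a mixed model. Resample patients, not segments, for any AUC interval.

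The cost is revised wording and slightly more analysis work, with no extra data or patients. Patients without an identified exit site drop out of the contrast, intervals may be wider, and at an ICC of 0.1 no power is gained.
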